4.3.16 ESTIMATED VISIT DURATION

The total duration of the inpatient visit is approximately 10-12 hours depending on the visit. The study time may be extended for glucose stabilization prior to discharge.

4.4 SENSOR REMOVAL

All sensors will be removed approximately 180 days post insertion. Removal of the Sensor may also be scheduled after the Day 180 accuracy visit if more convenient for subject and clinicians. Sensor removal before or after the specified visit will not be considered a protocol deviation provided that removal is performed no longer than 189 days post-insertion and Visit removal procedures/activities are followed.

Subjects will be asked to complete *Diabetes Distress Scale* and *CGM Satisfaction* questionnaires related to their experiences at the end of sensor wear period.

Prior to Sensor removal, the Investigator will assess the Sensor location visually as well as by palpation. The Sensor will be removed following the procedure in the Eversense® CGM Sensor Insertion and Removal Instructions.

The removed Sensor(s) will be handled in compliance with institution/regulatory requirements for biomedical waste, and will be returned following Eversense® instructions, using the provided Biohazard Return Kit.

4.4.1 Day 180 Sensor Removal and Insertion (2 Sensor Subjects)

For subjects with 2 sensors, only the primary sensor will be removed approximately 180 days post insertion. A new Eversense 180 sensor will be inserted in the same arm. The secondary sensor will remain in situ. The Investigator will determine if the initial incision created for the removal of the primary sensor is adequate for the insertion of the new sensor per recommendations of Deiss D, et all¹³. Based on Investigator discretion, a new incision and insertion location may be used for placement of the new sensor. Based on recommended practices, durable performance of multiple sensor cycles is expected with consecutive insertions^{14,15}. Both sensors will be removed 365 days post insertion of the secondary sensor. Sensor removal before or after the specified visit will not be considered a protocol deviation provided that removal is performed no longer than 374 days post-insertion for the secondary sensor and Visit removal procedures/activities are followed.

4.5 POST-SENSOR REMOVAL FOLLOW UP, VISIT 12 AND VISIT 16

Subjects will return to the clinic approximately 10 days following Sensor removal (sensor removal date +7 to +17 Days). The healing of the Sensor site will be evaluated at this planned final visit. If there is a concern by the investigator about healing of the Sensor site, the subject will be asked to return to the clinic in approximately 10 days, and followed until resolution. Any adverse event would be reported. Clinicians may request photographic images as part of the follow-up process if subjects are unable to return to the clinic.

Subjects will exit the study after the Follow-up Visit 12 is completed as above. The subset of subjects with 2 sensors completing additional visits 13-15 will exit the study after Follow-up Visit 16. Subjects will continue to follow their diabetes care routine according to their health care provider recommendations.

5 GENERAL CONSIDERATIONS FOR STUDY VISITS

5.1 DEFINITION OF ENROLLMENT

A subject is considered enrolled in the clinical trial after he or she has provided informed consent.

Subjects who fail one or more of the eligibility criteria are considered screen failures. Subjects who withdraw consent or are withdrawn by the investigator after enrollment and prior to the first Sensor insertion attempt are “withdrawn prior to Sensor insertion” and are withdrawn from the study without data acquisition. A listing of screen failures and “withdrawals prior to Sensor insertion” subjects including the reason for study exit will be reported.

Subjects who begin a first Sensor insertion procedure (defined as injection of local anesthetic) remain enrolled in the study and will be analyzed as evaluable subjects per the description of study populations in Section 11 Statistical Methods.

5.2 MEASUREMENT DEVICES– MAINTENANCE/CONTROL TESTING

Study equipment (bedside YSI glucose analyzer, ketone meter and study-supplied (SMBG) meter) are described in detail below.

5.2.1 BEDSIDE YSI

The primary instrument for plasma glucose measurements is the YSI glucose analyzer (2300 Stat Plus Glucose & Lactate Analyzer, Yellow Springs Instruments, Yellow Springs,

Senseonics, Inc.

Confidential Information

Page 47 of 94

Protocol #: CTP-0036 , Version 09

Effective Date: 14 Apr 2020

OH, USA). Manufacturer instructions for operation, calibration, quality control, and maintenance will be followed.

5.2.2 SUBJECT SMBG METER

The study will supply and use a widely-used, commercially available FDA-approved self-monitoring blood glucose (SMBG) meter and strips. Control solution testing of the meter/strips will be verified with the control solution(s) specific to the meter and strips. The tested control solutions must read within the established range on the glucometer strips per manufacturer labeling in order to be used in the study. Manufacturer instructions for operation and quality control will be followed. Subjects will be advised to perform control solution testing each time a new package of strips is deployed, or any time the subject suspects improper performance of the meter.

5.2.3 KETONE METER

The study will supply and use an FDA-approved self-monitoring ketone meter and strips (Abbott Precision Xtra or similar), which will measure β -hydroxybutyrate (β -HOB). Ketone meters will remain at the clinical site (not disbursed to the subject). Calibration of the ketone meter will be verified with the control solution(s) specific to the meter and strips. The tested control solutions must read within the established range on the strips per manufacturer labeling in order to be used in the study. Manufacturer instructions for operation and quality control will be followed.

5.3 SENSOR REPLACEMENT

Primary sensors that fail within 30 days of sensor insertion will be replaced at an unscheduled visit. Subjects will continue to follow their originally scheduled visits.

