11.1.7 SUBJECT ACCOUNTABILITY

A Subject Accountability flow diagram will account for all subjects from informed consent through end of study and includes any early explants or withdrawals (Figure 1 in APPENDIX 1).

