11.3.2.2 SAMPLE SIZE AND POWER CALCULATION

This study does not feature any inferential statistics. The sample size for the study was not determined based on a power calculation but was based on the desire to obtain a minimum number subjects at the 180 day visit (i.e. 120)

Additionally, the enrollment target of 20 patients per subgroup of interest (based on type of diabetes (type 1 vs. type 2), age (≥ 65 years of age vs. < 65), and baseline HbA1c ($\geq 8\%$ vs. $< 8\%$) will provide a clinically reasonable amount of data to characterize these subgroups. A subgroup of size 20 will provide an 80% probability of observing one or more rare events in that subgroup for a subgroup population rate as low as 8%.

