11.3.2.6 STABILITY OF THE SYSTEM THROUGHOUT SENSOR LIFE

For the full 180 day duration of the study, performance of the system overtime will be assessed by visit number (Table 8 in APPENDIX 1).

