161-200											
201-250											
251-300											
301-350											
351-400											

Table 8. CGM System Accuracy by Visit Number (Sample Table)

Day Number	Number of Paired CGM-YSI	Mean Absolute Relative Difference (%)	Median Absolute Relative Difference (%)	Percent of CGM System Readings Within				
				Percent 15/15% of Reference	Percent 20/20% of Reference	Percent 30/30% of Reference	Percent 40/40% of Reference	Percent Greater than 40/40% of Reference
Day 1								
Day 7								
Day 14								
Day 22								
Day 30								
Day 60								
Day 90								
Day 120								
Day 150								
Day 180								

Table 10: CGM System between System Precision

Level of Mean Glucose	Mean Difference (Sensor 1 - Sensor 2) (mg/dL)	SD of Difference (mg/dL)	N Pairs
<= 70			
71-180			
> 180			
All			

PARD	
PCV	

Confidential

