6.1.2 Study Day

Day 0 (Visit 2 in the study schedule) is the date of insertion of the Sensor. Day in study will be calculated as Study Day = Visit Date – Date of insertion of the Sensor.

Duration in study will be based on last study contact date, which is the latest date of all follow-up visits or assessments, adverse event onset or resolution, or study exit including date of death. It will be calculated as Duration Days = Study Exit – Date of insertion of the Sensor.

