6.1.3 Visit Windows

Unless otherwise specified, visit based assessments will be analyzed for each analysis time point according to the nominal visit entered in the Case Report Form (CRF) regardless of if it is out of window.

Statistical Analysis Plan		Page 14 of 28
Sponsor Senseonics, Incorporated	Study PROMISE Study: A Prospective, Multicenter Evaluation of Accuracy and Safety of an Implantable Continuous Glucose Sensor Lasting up to 180 Days	Version 3.0

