6.2 Analysis Populations

The following analysis populations are defined for analysis:

1. Per-protocol effectiveness analysis population: This is based on laboratory reference values which are equilibrated with capillary blood glucose values¹, obtained at 15 minutes intervals with matching CGM pairs from measurements, and which are free from protocol deviations, which include:
 - a. Protocol deviations that were not identified at intake (e.g. hematocrit out of window, visit out of window, recent use of tetracycline/sorbitol/mannitol, DKA or Severe hypoglycemia during the past 30 days)
 - b. Flagged reference measurement as indicated in source documentation (e.g., expired membrane, expired calibration, dilute sample)
2. Evaluable analysis population: This is based on data from participants with a minimum of three paired glucose readings since a smaller number of data points from a subject would not be considered representative of intended clinical use. A measurement from the reference test is paired with a reading from the Sensor that took place within a 5-minute period after sample acquisition.
3. Safety analysis population: This is based on data from participants who have undergone the Sensor insertion procedure at day 90 and day 180 visits.

The Per-protocol effectiveness analysis population will be considered the primary analysis set for effectiveness evaluations for the primary sensor configuration described in G180235. The Safety analysis population will be considered the primary analysis set for safety evaluations. Analysis of additional populations will be considered supportive in nature, in particular for the SBA sensor configuration, as described in G180235 S006.

¹ Liu D, et al, "Aterial, arterialized venous, venous and capillary blood glucose measurements in normal man during hyperinsulinaemic euglycaemia and hypoglycaemia", Diabetologia, 1992, 35:287-290.

Statistical Analysis Plan		Page 15 of 28
Sponsor Senseonics, Incorporated	Study PROMISE Study: A Prospective, Multicenter Evaluation of Accuracy and Safety of an Implantable Continuous Glucose Sensor Lasting up to 180 Days	Version 3.0

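### The by-visit accuracy table hides the age of replacement sensors, which are younger than the study day of the visit by the day of replacement (147-181 days old in the Day 180 row if replaced on days 1-30)

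*Protocol*

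**What the plan says.** Protocol 5.3 covers primary sensors that fail within 30 days of insertion: they "will be replaced at an unscheduled visit. Subjects will continue to follow their originally scheduled visits". It limits the day of failure. It sets no deadline for the replacement visit and does not say whether a replacement may itself be replaced.

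SAP 6.1.2 fixes the time origin: "Day 0 (Visit 2 in the study schedule) is the date of insertion of the Sensor". No second origin is given for a replacement. Under SAP 6.1.3, visit-based data are "analyzed for each analysis time point according to the nominal visit entered in the Case Report Form (CRF"), in window or not.

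Protocol 11.3.2.6, under a heading about stability over the life of the sensor, states that "performance of the system overtime will be assessed by visit number". It points to Table 8, titled "CGM System Accuracy by Visit Number (Sample Table"), with rows from Day 1 to Day 180. SAP Table A.9 has the same layout.

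Three other places bear on the point:

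- SAP 6.2 removes deviations from the per-protocol effectiveness set, for example "hematocrit out of window, visit out of window".
- Protocol 11.1.7 plans a flow diagram that "includes any early explants or withdrawals".
- Protocol 11.1.3 summarises time from insertion to end of life or to the end of planned visits, whichever is earlier, as one distribution. SAP 6.10 lists sensor longevity without naming a method.

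Protocol 5.4 withdraws a subject whose primary sensor shows a sensor-replacement alert.

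**The concern.** The study is meant to describe accuracy through about 180 days of sensor use, and the by-visit table is where a reader will look for drift with age. For a subject on the first sensor, study day and sensor age are the same. For a subject on a replacement they differ, and nothing in the pages available flags the replacement's pairs or tabulates accuracy by actual age. A reader of the Day 180 row cannot tell how many of its sensors are that old.

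The protocol itself treats age as relevant. A new sensor passes through warm-up and initialization before daily calibration (1.1.2), and the planned calibration analysis changes regime after Day 21 from insertion (11.3.2.8). A replacement read in the Day 22 or Day 30 row may be in a different phase from the rest of that row.

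The longevity summary has a related weakness that applies to every sensor. A time that ends because the sensor failed and a time that ends because the visits ran out are entered alike.

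**Working it through.** **1. The plan's own window.** Protocol 3.3.3 gives Visit 11 as -3/+2 days: 180 - 3 = 177 and 180 + 2 = 182, which is the day 177-182 window in SAP 4.3. The same arithmetic reproduces the other eight SAP windows from Day 7 on.

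**2. Age of a replacement at each visit.** Age = v - r, where v is the visit's study day (SAP window) and r the day of replacement, taken as 1 to 30. Ages below 1 day are dropped because no glucose is calculated in the first 24 hours (Protocol 1.1.2). For the same reason the Day 1 row is not affected.

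| Row | Window (v) | Age of replacement sensor (days) |
|---|---|---|
| Day 7 | 6-8 | 1-7 |
| Day 14 | 13-15 | 1-14 |
| Day 22 | 21-23 | 1-22 |
| Day 30 | 27-37 | 1-36 |
| Day 60 | 53-67 | 53 - 30 = 23 to 67 - 1 = 66 |
| Day 90 | 83-97 | 53-96 |
| Day 120 | 113-127 | 83-126 |
| Day 150 | 143-157 | 113-156 |
| Day 180 | 177-182 | 177 - 30 = 147 to 182 - 1 = 181 |

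**3. Separating replacement from window spread.** Original sensors can also be younger than the nominal label; the Day 60 row admits one aged 53 days. The effect of replacement is the gap from study day: v - (v - r) = r, so 1-30 days whatever the visit day.

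**4. The Day 180 row.** 182 - r is at least 177 only for r of 5 or less. There are 6 visit days x 30 replacement days = 180 combinations. Those below 177 days number 25 x 6 = 150 (r = 6 to 30) plus 1 + 2 + 3 + 4 + 5 = 15 (r = 1 to 5), in total 165. Three combinations give 180 or 181 days. These are counts of calendar combinations, not probabilities.

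**5. 147 days is not a floor.** If the replacement visit came 7 or 14 days after a day-30 failure (assumed delays), the ages would be 177 - 37 = 140 and 177 - 44 = 133.

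**6. Weight in the Day 180 row.** Protocol 11.1.4, which assumes 160 inserted, plans 5600/112 = 6000/120 = 50 pairs per subject. One replacement therefore supplies 50/6000 = 0.83% to 50/5600 = 0.89% of the row. The shift in the row's MARD is p x d, with p the share of replacements and d the MARD difference between replacement and original sensors. Neither is in the documents. With assumed p of 2%, 5% and 10% and assumed d of 1-4 points, the shift is 0.02-0.08, 0.05-0.20 and 0.10-0.40 points.

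**7. The pooled primary MARD.** Protocol 11.3.2.1 averages over all pairs with no day label. Relabelling by sensor age moves no pair in or out.

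**8. Whether another rule catches it.** The out-of-window exclusion does not, because the visit is in window on the original calendar. SAP 6.1.2 computes study day from the insertion date without saying which insertion counts when there are two; even if the second were used, the row would still follow the nominal visit. The flow diagram and the deficiency tables can show that sensors failed early, but they are not linked to the visit rows.

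**9. Longevity.** Take a sensor inserted on day 30 and still working at a day-177 Visit 11. If its time is closed there, it enters the Protocol 11.1.3 distribution at 147 days, exactly as would a sensor that reached end of life at 147 days. Any original sensor still working when its visits end is treated in the same way.

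**The case against.** The best defence is that the table does what its title says. The body of Protocol 11.3.2.6 speaks of the study's duration and SAP 6.6.4 of the study period; only the protocol heading speaks of sensor life. The analysis is descriptive, no acceptance threshold hangs on the Day 180 row, and replacements may be few. It is also true that if Protocol 5.4 governs early failures that raise the alert, fewer replacements reach later rows. All of this stands, and it limits the point to labelling and counting. It does not answer it: the heading invites a sensor-age reading, and the table would not reveal whether replacements are few or many.

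Three stronger inferences are tempting and should not be drawn.

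- **That replacements threaten the target of 120.** Protocol 11.3.2.2 rests the size on the "desire to obtain a minimum number subjects at the 180 day visit (i.e. 120"), and SAP 5 counts participants followed up. With SAP Day 0 at Visit 2, a subject with a replaced sensor who attends Visit 11 counts under both.
- **That every replacement is younger than its row label.** A sensor aged 180 or 181 days is not. What always holds is that it is younger than the study day of its visit.
- **That late accuracy is materially flattered.** The replacement rate and the MARD difference are both unstated, so the documents do not support this.

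It may also be said that Kaplan-Meier is only a preference in a descriptive study, and that Protocol 11.1.3 already counts from insertion. The second part is right. The first is not a full answer, since the present summary cannot separate failures from working sensors.

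**Conclusion.** The point holds as one of labelling and counting. From the Day 7 row on, a replacement sensor is younger than its visit's study day by the day of replacement: 1-30 days if replaced on days 1-30. In the Day 180 row that means 147-181 days old, and under 177 days if replaced on day 6 or later. The ages assume in-window visits and replacement on days 1-30; a later replacement visit would lower them.

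The number of sensors affected is unknown. The effect on the Day 180 MARD is probably small: 0.02-0.40 points under the assumed inputs in the working. The pooled primary MARD is unaffected. Separately, and for all sensors, the Protocol 11.1.3 summary does not distinguish failure from the end of observation. The absence of a flag is judged on the pages available; some appendix pages were not.

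**What to change.** 1. In SAP 6.1.2, 6.1.3 and Table A.9, define sensor age from each sensor's own insertion date, identified by serial number. Keep the all-sensor by-visit rows and add the number of replacement sensors and of their pairs to each. Add a supportive tabulation by actual sensor age, or rows without replacements with a note that these are conditional on survival of the original sensor. At Visit 11, report how many of the sensors read are at least 177 days old.
2. For longevity (Protocol 11.1.3, SAP 6.10), use a Kaplan-Meier estimate from each sensor's own insertion, with end of life as the event and censoring at study completion or at withdrawal for reasons unrelated to the sensor.
3. Keep all pairs in the primary MARD.
4. Reconcile Protocol 5.3 and 5.4 for an early failure that shows a sensor-replacement alert. The text does not say which applies, and the answer decides which subjects reach the later rows.

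Serial numbers are recorded at insertion (Protocol 4.2.3) and identified at each transmitter download (10.2.2), so the analysis changes need no new data. The cost is SAP wording and a little more tabulation.

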5.4 PRIMARY SENSOR BLINDING

During the study the primary system may go into a “blinded mode” (called Clinical Mode by the device). Under these circumstances subjects will continue to wear the system, and enter calibrations (as prompted) and SMBG values, but the system will not provide sensor glucose information or glucose related alerts. Subjects should continue with all remaining sensor accuracy visits with the blinded system.

If a primary sensor displays a “sensor replacement” alert, it (and the secondary sensor if applicable) will be removed at an unscheduled visit, and the subject will be withdrawn.

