3.3 STUDY DESIGN

3.3.1 OVERVIEW

This is a prospective, multi-center study, whereby approximately 210 subjects will be enrolled, and 180 subjects will be inserted in the United States at up to 15 sites. The investigation will include both clinic visits and home use of the Eversense® 180 CGM System. A minimum of 80 subjects, will have two Sensors inserted by trained Investigators. The Sensor(s) will be inserted in the upper arms of the subjects. The accuracy of the Eversense® 180 CGM System will be evaluated during clinic visits comparing Sensor glucose values and plasma glucose values measured on a bedside glucose analyzer. For qualifying subjects, during the clinic visits, there will be planned hyperglycemia and hypoglycemia challenges, as described in Section 4.3.

In this study, including the clinic and home settings, all diabetes care decisions will be based on SMBG blood glucose values and clinical standard of care, rather than Eversense® 180 CGM System results.

To ensure adequate numbers of subjects for specific scenarios of interest, there will be two randomizations:

- Shift of the Day 1 sensor accuracy assessment: early (hours 1-8) vs. middle (hours 9-16) vs. late (hours 17-24)
- Day of the Visit 4 accuracy assessment: Day 7 vs. Day 14

Shift of the Day 1 assessment will be for the Day 1 of sensor life (the day after insertion). Both randomizations are independent of one another.

The Subject visit schedule includes 12 visits over a period of approximately 8 months (inclusive of visit windows from screening visit through follow-up visit). For the subset of subjects inserted with 2 sensors, the subject visit schedule includes 16 visits over a period of approximately 14 months.

The study is anticipated to take approximately 26 months, including the enrollment period.

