11.1.3 SENSOR EVALUATION PERIOD

The Eversense® 180 CGM System performance will be evaluated in the period after insertion. The Transmitter will assess the Sensor's signal sensitivity in real time for any premature failure independent of the expected lifetime based on time from insertion. If the measurement of potential degraded response of the Sensor optical system signal drops below a pre-defined percent of its original value and/or systemic patterns in Sensor accuracy to entered calibration points drops below a pre-defined threshold, then the device has reached its end of life (sensor retirement) and will no longer provide glucose readings. This end of life determination marks the end of the accuracy evaluation period for this Sensor. The distribution of times between Sensor insertion and end of life or completion of scheduled study visits, whichever occurs first will be summarized.

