11.1.4 EXPECTED PAIRED POINTS BY RANGE*

The expected number of paired YSI/sensor points by YSI glucose range are targeted as follows:

	Day 1	Day 7	Day 14	Day 22	Day 30	Day 60	Day 90	Day 120	Day 150	Day 180	Total through 180 days
YSI Range / Min # of subjects	160	80	80	160	160	160	155	140	130	112-120	
40-70 mg/dL	1040	520	520	1040	1040	1040	1008	910	845	728-780	8691-8743
71-299 mg/dL	4400	2200	2200	4400	4400	4400	4263	3850	3575	3976-4260	37664-37948
300-400 mg/dL	1280	640	640	1280	1280	1280	1240	1120	1040	896-960	10696-10760
Total	6720	3360	3360	6720	6720	6720	6510	5880	5460	5600-6000	57050-57450
										Total paired points	57050-57450

*Estimates based on 160 subjects inserted, with challenge type distributed equally

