6.6.4 Other Effectiveness Endpoints

The means and medians of absolute relative difference, absolute difference and relative difference when the reference measurements (Yellow Springs Instrument analyzer) will be presented.

The agreement between the Sensor and the reference measurements at different ranges of reference measurements and of Sensor measurements will also be presented.

Statistical Analysis Plan		Page 18 of 28
Sponsor Senseonics, Incorporated	Study PROMISE Study: A Prospective, Multicenter Evaluation of Accuracy and Safety of an Implantable Continuous Glucose Sensor Lasting up to 180 Days	Version 3.0

Concurrence of the Sensor and the reference standard (Yellow Springs Instrument analyzer) will be presented as Tables. Performance of the Eversense® 180 CGM System over the study period will be assessed by visit.

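### Stability is judged only from accuracy by visit, and the later rows under-represent sensors retired early, so a flat by-visit MARD could partly reflect changing composition

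*Protocol*

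**What the plan says.** Protocol 11.3.2.6, the section on stability throughout sensor life, contains one analysis: "performance of the system overtime will be assessed by visit number". SAP 6.6.4 repeats it: "Performance of the Eversense® 180 CGM System over the study period will be assessed by visit". The shells (Protocol Table 8, SAP A.9) have one row per visit day and a column for the number of CGM-YSI pairs. They have no column for sensors or subjects.

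Protocol 11.1.3 gives two triggers for end of life, joined by and/or. One is a fall in the optical signal. The other is that "systemic patterns in Sensor accuracy to entered calibration points drops below a pre-defined threshold". The consequence is stated: "This end of life determination marks the end of the accuracy evaluation period for this Sensor". Under Protocol 5.4, a primary sensor that shows a replacement alert, together with any secondary sensor, "will be removed at an unscheduled visit, and the subject will be withdrawn". Subjects who leave are not replaced (Protocol 7.6.6, SAP 4.3), and SAP 6.3 uses available data without imputation.

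The table in Protocol 11.1.4 gives the expected minimum number of subjects per visit, falling from 160 at Day 1 to 112-120 at Day 180. Its footnote reads "Estimates based on 160 subjects inserted, with challenge type distributed equally". Protocol 3.3.1 now says that "approximately 210 subjects will be enrolled, and 180 subjects will be inserted".

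Some disclosure is planned. Protocol 11.1.3 summarises the time from insertion to end of life or completion. Protocol 11.1.7 has a flow diagram that includes early explants. SAP 6.4 reports accountability by visit and early exits by reason.

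**The concern.** A reader will judge stability by looking down the rows from Day 1 to Day 180. That comparison is clean only if the rows hold much the same sensors, or if sensors leave for reasons unrelated to accuracy. Here one of the two retirement triggers is poor accuracy itself. A sensor retired at, say, Day 100 adds pairs to the early rows and none to the later ones. If such sensors were less accurate than the rest, their departure lowers the later MARD, and a real worsening in the remaining sensors could be offset in part.

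This matters most in the second half of wear. Protocol 8.2 notes that the system is already approved for up to 90 days, so Days 90 to 180 carry the new claim, and the plan expects most of its losses there.

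**Working it through.** **1. Reproduce the plan's table (Protocol 11.1.4).** Total pairs divided by subjects gives 42 per subject at every visit through Day 150 (for example 6720/160 = 42 and 5460/130 = 42). At Day 180 it gives 50 (5600/112 and 6000/120). The visit totals sum to 57050-57450, as stated.

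**2. Expected loss, all causes.** Loss = 1 - n at visit / n at start.

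| Visit | Subjects | Loss from 160 | Loss if 180 start and counts stay as printed |
|---|---|---|---|
| Day 90 | 155 | 3.1% | 13.9% |
| Day 120 | 140 | 12.5% | 22.2% |
| Day 150 | 130 | 18.8% | 27.8% |
| Day 180 | 112-120 | 25.0-30.0% | 33.3-37.8% |

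The table has not been updated to 180 inserted, so the last column is conditional. From 160, the total loss is 40-48 subjects, of whom 5 are lost by Day 90 and 35-43 afterwards.

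**3. What the pair column would show.** From Day 1 to Day 180, pairs fall from 6720 to 5600-6000. That is 1 - 6000/6720 = 10.7% to 1 - 5600/6720 = 16.7%. The loss of subjects is 25-30%. The pair count understates the loss because the Day 180 session is longer (50 pairs against 42).

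**4. Possible size of the composition effect.** The documents give neither the between-sensor SD of MARD nor its relation to loss, so both are assumed. Suppose a sensor's MARD and its tendency to be lost are jointly normal with correlation rho, and a fraction f with the highest tendency is lost. Then the retained sensors have a mean MARD lower than that of all sensors by

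shift = rho x SD x phi(z)/(1 - f), with z = Phi^-1(1 - f).

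- f = 0.25: phi(z)/(1 - f) = 0.424. With rho = 0.3 and SD = 2, shift = 0.6 x 0.424 = 0.25. With rho = 0.7 and SD = 3, shift = 2.1 x 0.424 = 0.89.
- f = 0.30: phi(z)/(1 - f) = 0.497. The same inputs give 0.30 and 1.04.
- rho = 0 gives no shift.

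**5. Dependence on the retirement share.** A second illustration lets only part of the loss be retirement. Let L be the loss, q the share of it due to retirement, and gap the MARD of retired minus surviving sensors. The Day 180 row then understates the MARD of retired and surviving sensors together by w x gap, with w = Lq/(Lq + 1 - L). For an assumed gap of 2 points and L = 0.25-0.30:

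- q = 1: 0.50-0.60 points
- q = 0.5: 0.29-0.35 points
- q = 0.25: 0.15-0.19 points

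The answer scales directly with the gap, which is unknown.

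**The case against.** The strongest reply is that the plan measures what it should. The device is meant to last up to 180 days or until its own end-of-life indicator, after which it gives no reading. Accuracy at Day 180 among sensors still reporting is what a Day 180 user experiences. This stands, and for the same reason a reader should not infer that the pooled MARD is wrong because longer-lived sensors contribute more pairs. Weighting by time in use is a choice of estimand. What does not follow is that a comparison between rows shows how sensors change over time.

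A second reply is that attrition is disclosed through the flow diagram, exits by reason, the time-to-end-of-life summary and the pair counts. That is true, but none of these is linked to accuracy, and the pair counts understate the loss (step 3).

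A third reply concerns two tempting overstatements, and it is right on both.

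- A reader might infer that the later rows contain only survivors. They do not. Systems in Clinical Mode stay in the accuracy visits (Protocol 5.4), primary sensors failing within 30 days are replaced on the same visit schedule (5.3), and a secondary sensor becomes primary if the first is lost to infection (7.3). A replaced sensor is younger than its row's day suggests, which is a further reason not to read the rows as sensor age.
- A reader might infer that 25-30% of sensors are expected to retire for inaccuracy. The figure is a planning count for loss of any kind, and retirement can occur on optical signal alone.

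Finally, the study is descriptive and commits to no claim of a flat trend. That limits the consequence, but a descriptive trend is still affected by who remains in it.

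**Conclusion.** The point holds as a limitation of the stability analysis. The rows compare partly different sensors, departure can depend on accuracy, and neither document plans a same-sensor comparison or reports accuracy before loss. A flat by-visit MARD would therefore be compatible with some drift combined with the loss of poorer sensors.

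The documents do not show that this will happen or how large it would be. The 25-30% is all-cause, on 160 inserted, with no stated retirement share. The 0.25-1.0 point range rests wholly on the assumed SD of 2-3 and correlation of 0.3-0.7, and should be read as an illustration, not an estimate of hidden drift. The overall MARD remains a valid description of the pairs collected. This is an inexpensive improvement worth making before analysis; it does not invalidate the endpoint.

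**What to change.** Amend SAP 6.6.4 and A.9, and Protocol Table 8 to match:

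- Add the number of sensors contributing to each row.
- Beside the all-subject rows, give the same statistics for (a) original primary sensors with pairs at Day 180, including within-sensor change, and (b) sensors lost before Day 180.
- For (b), report accuracy at the last visit before loss, by reason: replacement alert, infection, other withdrawal.
- Classify sensors replaced under Protocol 5.3 and secondary sensors promoted under 7.3 by the actual sensor and its age, not by the subject's visit day. A replacement alert in the first 30 days could fall under both 5.3 and 5.4, which lead to different outcomes; the two sections must be reconciled before such sensors can be classified.
- Word any stability statement as applying to sensors still in use, and present (a), (b) and the time-to-end-of-life distribution together. Group (a) is itself conditioned on surviving to Day 180, so it cannot carry the statement alone.

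The cost is SAP wording and some extra rows and columns from data already collected. SAP section 7 already provides for an amended plan before analysis. Results for sensors later lost may look less favourable than the all-subject rows.
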